9.2.4.2 Vaccinee selection

Vaccinees will be primarily recruited by the qualified HCPs who will participate in the HCP survey. In the event that the target sample size of vaccinees is not achieved, then the possibility of recruitment by HCPs who have not participated in the HCP survey will be explored.

Each HCP who has agreed to recruit vaccinees will systematically distribute a kit containing a simplified guide for taking the web or paper questionnaire (as needed) to eligible vaccinees (or their parents/guardians if vaccinees are younger than 18 years old). To limit selection bias, an HCP will be requested to consecutively solicit vaccinees for participating in the survey and a maximum of 10 vaccinees per centre will be recruited.

Vaccinee anonymity will be maintained throughout the study. A unique number will be printed on each page of the questionnaire, which will link each questionnaire with the corresponding HCP who will distribute it. However, no log would be kept at the HCP level which would provide linkage between material for the web/paper survey distributed to the vaccinees (or their parents/guardians if vaccinees are younger than 18 years old) and vaccinee identity. When a vaccinee (or their parent/guardian if vaccinee is younger than 18 years old) fills in the survey on the web/paper, the unique number for the vaccinee survey will ensure that no more than 10 vaccinee questionnaires originate from the same YFVC. Vaccinee recruitment will also be competitive.

Selection bias is reduced through 1) consecutive recruitment of vaccinees by each enrolled qualified HCP, 2) the cap on the number of vaccinees who could be recruited per centre, and 3) the recruitment through both participating HCPs and non-participating HCPs (if the target vaccinee sample size is not achieved) in the survey. As there will be no information linking the vaccinees' identities with the recruiting HCP, there would be no incentive for HCPs to recruit their best vaccinees. There will be incentive for the vaccinees. As there will be no information linking the vaccinees' identities with the recruiting HCP, vaccinees will be unlikely to worry about the answer they provide about the use of the checklist by their HCPs.

Vaccinee recruitment by non-participating HCPs in the survey (if needed):

Qualified HCPs who do not participate in the survey will be contacted and will be asked a few screening questions in order to confirm their eligibility to help with vaccinees' recruitment. Vaccinees will be recruited using the same methods, as used by the participating HCPs in the survey.

9.3 VARIABLES

9.3.1 HCP questionnaire

The following variables will be collected through the HCP survey:

- Variables related to HCPs' practice:
 - o Demographic information (age range, gender and region)

- o HCP profession (physician, nurse or pharmacist)
- Type of work setting (General Practice [National Health Service], General Practice
 [Private], pharmacy, travel clinic, occupational health department, hospital or other)
- Years of experience in the profession
- Prescriber administering STAMARIL® under a Patient Group Direction (PGD)⁴
- Experience with STAMARIL[®] (whether providing consultation and/or administering STAMARIL[®], years of experience in providing consultation and/or administering STAMARIL[®] and number of patients administered with STAMARIL[®] and/or provided consultation for the administration of STAMARIL[®] in the past 12 months)
- Yellow fever training sponsored by NaTHNaC or PHS (HCP trained ≤12 months ago or >12 months ago)
- Variables related to the HCPs' awareness, utilisation, and distribution of the aRMM materials:
 - Awareness of the UK (STAMARIL®) yellow fever pre-vaccination checklist by the HCPs
 - Use of the UK (STAMARIL®) yellow fever pre-vaccination checklist (Annex 3) by the HCPs
 - Use of the NaTHNaC/PHS yellow fever pre-vaccination checklist⁵ by the HCPs (Annex 4)
 - O Distribution of STAMARIL® PIL by the HCPs to yellow fever vaccinees
- Variables related to the knowledge and understanding of the key safety messages in any standardised yellow fever pre-vaccination checklist(s)
 - o Indications (e.g. yellow fever activity at travel destination) and contraindications (e.g. hypersensitivity to vaccine components, immunosuppression [congenital or acquired], thymus dysfunction, thymoma, thymectomy, or age less than 6 months), or precautions

⁴ Patient Group Directions (PGDs) provide a legal framework that allows some registered HCPs to supply and/or administer specified medicines to a pre-defined group of patients, without them having to see a prescriber (such as a doctor or nurse prescriber)

⁵ Note: In addition to the checklist developed by MHRA, NaTHNaC/PHS has also issued a checklist which aligns with the Green Book (the Green book has the latest information on vaccines and vaccination procedures for all the vaccine preventable infectious diseases that may occur in the UK) and is intended for travellers to read and complete for yellow fever consultation with HCPs; both checklists are similar in content.

(e.g. infants from 6 up to 9 months of age, advanced age, pregnancies and breastfeeding)

 Possible side effects (including signs and symptoms of yellow fever vaccine-associated viscerotropic disease and yellow fever vaccine-associated neurotropic disease; hypersensitivity).

9.3.2 Vaccinee questionnaire

The following variables will be collected through the vaccinee survey:

- Variables related to vaccinees' demographic information (age range, gender, region and education level)
- Variables related to vaccinees' receipt of the STAMARIL® PIL

9.4 DATA SOURCES

This will be a primary data collection survey conducted through two questionnaires administered primarily by web; a paper version (*if required*) is intended only for vaccinees:

- An HCP questionnaire (administered by web only)
- A vaccinee questionnaire (administered mainly by web; paper questionnaire is a supplement to web questionnaire)

9.4.1 Questionnaire description

The questionnaires have a disclaimer and consent at the beginning. They are designed to collect information on the eligibility and demographics of the participants. The questionnaires include open and closed questions on the contents of the checklist and STAMARIL[®] PIL, and the questions are in the order of exploring knowledge to awareness. The language of both questionnaires (HCPs and vaccinees) will be English.

The questionnaires are designed to be nondirecting, to avoid inducement of social desirability bias, and without any self-evident answers. Also, to avoid information bias, the web questionnaires will be programmed in such a way that the participants cannot go back to the previous questions.

A brief overview of the contents in each of these questionnaires is as below:

HCP questionnaire will include questions on:

- screening criteria, demographics
- awareness of the UK (STAMARIL®) yellow fever pre-vaccination checklist
- utilisation of any standardised yellow fever pre-vaccination checklist(s)
- distribution of the STAMARIL® PIL
- knowledge and understanding of key safety messages

Vaccinee questionnaire will include questions on:

• screening criteria, demographics

• receipt of the STAMARIL® PIL

9.4.2 Questionnaire pilot testing

The objective of each questionnaire will be tested among 3 HCPs and 3 non-HCPs, respectively, to make sure the right language and medical terms are used, and also to check the understandability of the language.

9.4.3 Time to completion

HCP questionnaire is estimated to take 10 to 15 minutes to complete. Vaccinee questionnaire is estimated to take up to 5 minutes to complete.

9.4.4 Approaches for increasing response rate

People are frequently contacted to participate in web or phone surveys. According to international studies, the overall response rate of participation remains low.¹⁹⁻²¹ Holbrook et al. showed that the response rate to surveys continues to decline over time, but a lower rate does not appear to reduce the representativeness of a demographic survey.²¹ Van Geest et al. conducted a systematic review of 66 published reports on efforts to improve response rates.²² Two general strategies were explored: incentive-based approaches and survey design-based approaches. Financial incentives, even little ones, were reported to be effective in improving physician response rates, while non-monetary incentives were much less effective. These measures include the use of a short questionnaire, as well as questionnaires personalised and endorsed by professional associations.

In order to increase the response rate among HCPs in the present survey, a compensation fee will be proposed to HCPs for their participation in the survey and/or vaccinee recruitment. Also, to increase the response rate among vaccinees (or their parents/guardians if vaccinees are younger than 18 years old), they will be immediately provided with material for the web/paper survey after the receipt of the vaccine and an honorarium after they complete the survey.

9.5 STUDY SIZE

9.5.1 Determination of sample size

The sample size formula based on the normal approximation of the binomial distribution, for calculating the number of participants required for a proportion is as follows:

$$n = \frac{P \cdot (1-P) \cdot \left(Z_{1-\alpha/2}\right)^2}{e^2},$$

where P is the expected proportion, e is one half the desired width of the confidence interval (CI), and $Z_{1-\alpha/2}$ is the standard normal Z value corresponding to a cumulative probability of $1-\alpha/2$ (e.g., if α =.05 then Z = 1.96). The following table provides the margin of error for 95% CI based on various sample sizes and proportions of interest.

Table 2 Margin of error for 95% CI based on various sample sizes and proportions of interest

Margin of error for 95% CI (absolute precision)							
Proportion of interest	8%	7%	5.7%	5%	4%		
10%	54	71	106	139	216		
30%	126	165	248	323	504		
50%	150	196	295	384	600		
70%	126	165	248	323	504		
90%	54	71	106	139	216		

As P is not known in advance, we consider it to be 50%. Such a hypothesis yields the most conservative i.e. the largest, sample size.

Based on 2019 figures,²³ a minimum sample size of 200 HCPs (a 7% precision) and 150 vaccinees (a 8% precision) are targeted assuming an expected proportion of interest of 50%. If the proportion of interest is greater than 50% which may be predicted from other sources such as an Annual Return Report, the precision could be further increased with the same sample size, or the sample size could be further decreased with the same precision. For example, based on the Annual Return 2020 report published by NaTHNaC, 90.7% of YFVCs supplied the yellow fever vaccine PIL routinely to travellers receiving yellow fever vaccination. In this case, a sample size of 200 HCPs will achieve a precision below 4%. If a similar proportion of vaccinees (or parents/guardians of minor vaccinees) can also confirm receipt of yellow fever vaccine PIL, a sample size of 54 vaccinees will achieve an 8% precision in this case.

9.5.2 Sample size feasibility

In 2019, there were 2,821 YFVC (5,474 HCPs) in England, Wales, and Northern Ireland.²³ However, the number of YFVCs and the frequency of travel, especially to endemic countries, have been significantly affected by the COVID-19 pandemic. There were 2,295 YFVC (3,763 HCPs) which remained designated in 2020,¹³ suggesting a 19% decrease compared to 2019. The average number of yellow fever vaccine doses given per centre decreased from 47 (median: 22) in 2019 to 13 (median: 5) in 2020, which corresponds to a decrease of 72%. Sales of the yellow fever vaccine went from around doses in 2019 in the UK, to around doses in 2020, representing a 71% fall.

The dynamics of vaccine centres, vaccinees and number of doses administered are still not stabilised. Therefore, a sample size feasibility assessment will be done before the start of fieldwork to predict the likelihood of achieving the desired sample size and to eventually adjust the sample size.

For this assessment, the updated number of YFVCs, the number of vaccinees and the sales of the vaccine will be estimated. The YFVC will be matched with the OneKey database and HCPs will then be identified through OneKey as detailed in Section 9.2.4. This will provide an actualised number of identified HCPs.

The number of vaccinees will be estimated using the most recent sales data of STAMARIL® received by the MAH at the time of the feasibility assessment.

For HCP survey, the number of HCPs that will be included in the survey will be estimated based on a response rate of 5-10%. Therefore, for a sample size of 200 HCPs, between 2000 to 4000 HCPs will have to be contacted. Using the results of this assessment of the actual numbers of HCPs at the time of the survey will allow us to adjust the target sample size.

For vaccinee sample size assessment, the number of vaccinees who will complete the web/paper questionnaires will be estimated using a process as presented in Table 3. Participation rates may vary around the figures presented in this table. However, with a yearly population of vaccinees of around (as presented for 2019) it is possible to recruit around 174 vaccinees, while only 37 could be recruited with a yearly population of (as in 2020). Using the most recent numbers of vaccinees at the time of the survey will allow to adjust the target sample size.

In case the desired number of completed vaccinee questionnaires is not achieved during the 12-week period, the data collection period may be extended up to 24 weeks.

Table 3 Example of assumptions for calculation of expected sample size for patients during 12 weeks

Assumptions		2020 (4)
A/ Number of vaccines sold as a proxy for number of vaccinees for 12 weeks (from March to May) (1)	45,984	11,396
B/ Number of active YFVCs	2,989	2,418
C/ Number of HCPs involved in vaccinations	5,668	3,905
D/ Number of vaccinees per center per week ((A/B/12) (2)	1.28	0.39
E/ Number of HCPs who participate in the survey (10% participation rate based on IQVIA experience (3))	567	391
F/ Number of HCPs who agree to distribute material among vaccinees (assumption 10% based on IQVIA		
experience ⁽³⁾)	57	39
Vaccinees response:		
Number of vaccinees who actually receive the survey invitation during 12 weeks fieldwork (F*D*12)	872	184
20% response rate from vaccinees	174	37
10% response rate from vaccinees	87	18

¹⁾ The real number of vaccinees is smaller due to waste and stock.

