5 AMENDMENTS AND UPDATES

DOCUMENT HISTORY

Number	Date	Section of study protocol	Amendment or update	Reason
1	31 May 2023	Refer to protocol amendment	Amendment	Refer to protocol amendment summary of
		summary of changes		changes

AMENDED PROTOCOL 1 (31 MAY 2023)

This amended protocol (amendment 1) is considered to be nonsubstantial based on the criteria set forth in Article 10(a) of Directive 2001/20/EC of the European Parliament and the Council of the European Union as well as the Medicines for Human Use (Clinical Trials) Regulations 2004 in the UK. This is because it does not significantly impact the safety or physical/mental integrity of participants, nor the scientific value of the study.

OVERALL RATIONALE FOR THE AMENDMENT

As stated in the study protocol v2.0, a minimal sample size of 150 vaccinees (an 8% precision) would be targeted assuming an expected proportion of interest of 50%. The vaccinee questionnaire collection started on 16 March 2023. As of 24 May 2023, only 9 vaccinees completed questionnaires within 2 months of vaccinee data collection, although 123 vaccinees clicked the survery link based on IQVIA tracking. According to some HCPs who agreed to distribute the survey flyers to vaccinees, there are three possible explanations for the extremely low response rate among vaccinees:

- Difficulty to follow up with vaccinees because HCPs do not see vaccinees after yellow fever vaccination
- Vaccinees lost interest in participation when they realize they would not receive an honorarium
- Vaccination on-demand varies and low season for yellow fever vaccination

For the vaccinee survey, the primary objective is "To verify the receipt of the STAMARIL® PIL by yellow fever vaccinees at the time they get vaccination consultation in the UK", and the secondary objective is "To evaluate the yellow fever vaccinees' knowledge and understanding of the key safety messages in the STAMARIL® PIL in the UK". To increase the response rate among vaccinees, the MAH will remove secondary objective, amend the study protocol on conducting and reporting this survery according to the rationale summarized in the table below, and in line with the following plan:

• Shorten the vaccinee questionnaire by removing four questions designed for secondary objective

31-May-2023

Version number: 3.0

Provide an honorarium to each vaccinee who participate in the survey

Section # and Name	Description of Changes	Brief Rationale

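### Table 3 multiplies a count of HCPs by vaccinees per centre, so the expected 12-week vaccinee yield is overstated by up to 1.9-fold (2019) and 1.6-fold (2020)

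*Protocol*

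**What the plan says.** Section 9.5.1 sets a minimum of 150 vaccinees, for 8% precision at an expected proportion of 50%. Section 9.5.2 then asks whether that is reachable and says that the number of vaccinee completes will be estimated by the process in Table 3. That table defines "D/ Number of vaccinees per center per week" as A/B/12, where B counts centres. F is the number of HCPs who agree to hand out survey material: 10% of the 10% of HCPs expected to take part. The next row is the "Number of vaccinees who actually receive the survey invitation during 12 weeks fieldwork (F*D*12"), followed by rows at 20% and 10% vaccinee response. The text draws the conclusion that, at the 2019 volume, "it is possible to recruit around 174 vaccinees, while only 37 could be recruited" at the 2020 volume.

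Section 9.2.4.2 describes distribution at the level of the HCP. Each agreeing HCP gives out kits and solicits vaccinees consecutively, and a number on the questionnaire links it to that HCP. Section 10.3.9 pays the individual HCP for recruiting. Section 9.2.4.1 allows up to three HCPs per centre in the HCP survey, possibly five.

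**The concern.** F and D have different units. Multiplying distributing HCPs by the weekly throughput of a centre credits each HCP with every vaccinee seen at that centre, including those seen by colleagues. Because the table lists more HCPs than centres, the product is too large unless something else in the design makes one HCP equivalent to one centre.

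The stake is the planning figure. Of the four 12-week yields in Table 3 (174, 87, 37, 18), only 174 exceeds 150, and the text repeats it as what could be recruited. Section 9.5.2 also uses this calculation, with updated volumes, to decide whether to adjust the target, so an error in the formula carries into that decision.

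**Working it through.** **Inputs (Table 3, 2019 then 2020).**
- A, "Number of vaccines sold as a proxy for number of vaccinees for 12 weeks (from March to May"): 45,984; 11,396.
- B, "Number of active YFVCs": 2,989; 2,418.
- C, "Number of HCPs involved in vaccinations": 5,668; 3,905.
- F = 10% × 10% × C: 56.68; 39.05 (printed as 57; 39).

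**Step 1: reproduce the printed figures.** D = A/B/12.
- 2019: 45,984/2,989/12 = 1.282. Invited = 56.68 × 1.282 × 12 = 872. At 20%, 174; at 10%, 87.
- 2020: 11,396/2,418/12 = 0.3927. Invited = 39.05 × 0.3927 × 12 = 184. At 20%, 37; at 10%, 18.

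All six values agree with the table, so this is the calculation that was done.

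**Step 2: test the formula at its limit.** If every HCP distributed, F would equal C and the formula would invite 5,668 × 45,984/2,989 = 87,199 vaccinees from a pool of 45,984. For 2020 it would invite 3,905 × 11,396/2,418 = 18,404 from a pool of 11,396. In the same way, 1% of HCPs are shown reaching 872/45,984 = 1.9% and 184/11,396 = 1.6% of vaccinees.

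**Step 3: put both factors on a per-HCP basis.** Throughput per HCP per week is A/C/12.
- 2019: 45,984/5,668/12 = 0.676. Invited = 56.68 × 0.676 × 12 = 460.
- 2020: 11,396/3,905/12 = 0.243. Invited = 39.05 × 0.243 × 12 = 114.

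| | Invited | 20% response | 10% response |
|---|---|---|---|
| 2019 printed | 872 | 174 | 87 |
| 2019 per HCP | 460 | 92 | 46 |
| 2020 printed | 184 | 37 | 18 |
| 2020 per HCP | 114 | 23 | 11 |

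The ratio of printed to per-HCP is C/B: 5,668/2,989 = 1.90 and 3,905/2,418 = 1.61.

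**Step 4: how far the assumption can bend.** The printed figures need each distributing HCP to reach 100% of a separate centre's vaccinees. The per-HCP figures put the share at 1/1.896 = 53% for 2019. The 2019 yield at 20% response stays above 150 only if the share is at least 150/174.4 = 86%.

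**Step 5: what this does to 150.**
- The target: 1.96² × 0.25/0.08² = 150. This is right and does not use Table 3.
- Response needed for 150 in 12 weeks at the 2019 volume: 150/872 = 17.2% as printed, 150/460 = 32.6% per HCP.
- Over 24 weeks at constant volume and 20% response, per HCP: 2 × 92 = 184 (2019) and 2 × 22.8 = 46 (2020).
- Half-width at 50%: 1.96 × √(0.25/92) = 10.2 points; 1.96 × √(0.25/23) = 20.4 points.

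**The case against.** The best defence is that one HCP may act for the whole centre. Eligible HCPs may give the consultation, administer the vaccine, or both, so a vaccinee may meet more than one HCP, and the limit of ten vaccinees is set per centre. If each distributing HCP covers a different, entire centre, F*D*12 is correct. This stands to the extent that 1.9 and 1.6 are upper limits of ranges starting at 1.0. It does not rescue the table, because no section states that arrangement and Section 9.2.4.2 describes individual distribution.

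The protocol is also cautious elsewhere. Table 3 is labelled an example, and three of its four yields already miss 150. The target may be adjusted, fieldwork may run to 24 weeks, non-participating HCPs may recruit, and all available data will be analysed if the minimum is missed. Section 9.5.1 adds that about 54 vaccinees give 8% precision if the proportion is near 90%. All of this limits the consequence, but the printed yields still do not follow from the described distribution.

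A reader might infer that the minimum of 150 is itself unsupported. It is not: it comes from the precision formula.

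A reader might also take the report in Section 5 that "only 9 vaccinees completed questionnaires within 2 months of vaccinee data collection" as confirming the smaller yields. The documents do not support that. The same sentence reports 123 clicks on the survey link, whereas the per-HCP 2020 scenario implies only about 114 × 69/84 = 94 invitations in the 69 days from 16 March to 24 May 2023. Section 5 gives other reasons for the low return, and the 2023 volume is not stated. That rate also cannot be projected forward, because version 3.0 shortened the questionnaire and added an honorarium.

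**Conclusion.** The unit mismatch is real and can be shown from the table alone. The expected vaccinee yield is overstated by up to 1.90-fold for 2019 and 1.61-fold for 2020. The full factors assume that each vaccinee is handled by one HCP and that each distributor reaches only their own vaccinees. That is the reading the text favours, though it is not stated outright.

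On that reading no Table 3 scenario reaches 150 in 12 weeks. Feasibility then depends on the 24-week extension, which gives about 184 at the 2019 volume with 20% response and about 46 at the 2020 volume. The 184 is optimistic, since it assumes constant volume and note 2 to Table 3 describes March to May as the most likely peak. At the 2020 volume the minimum was already out of reach as printed, even over 24 weeks (2 × 37 = 74).

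These figures keep the table's 10% HCP participation. The text says the HCP number "will be estimated based on a response rate of 5-10" per cent; at 5%, yields would halve on either basis. No endpoint, success criterion or analysis method is affected.

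**What to change.** In Table 3, replace D with vaccinees per HCP per week, A/C/12 (0.68 and 0.24), and restate the last three rows as 460/92/46 and 114/23/11. In the text of Section 9.5.2, change 174 and 37 to about 92 and 23. Beside the 8% target, give the precision expected at those sizes at a proportion of 50%: about ±10.2 points for 92 and ±20.4 for 23. Say that reaching 150 depends on the extension to 24 weeks.

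If the intention is instead that one HCP distributes for the whole centre, state that in Section 9.2.4.2, limit distribution to one HCP per centre, and keep the printed figures.

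Either route costs a table and text edit. The first makes the stated yields less favourable but asks for no extra recruitment; the second also fixes how kits are distributed.
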